9.4.3 ANALYSIS OF THE SECONDARY EFFICACY ENDPOINTS

The secondary efficacy endpoints will be tested for statistical significance sequentially provided the primary endpoint is found to be statistically significant. The ITT population will be used. The first endpoint tested will be FOIS at 7 days following the last investigational treatment. The second endpoint tested will be DSRS at 7 days following the last investigational treatment.

Analysis details are specified in the SAP.

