4. STATISTICAL METHODS

4.1. Statistical Hypotheses

The primary efficacy analysis is based on an ordinal logistic model of PAS (1-8 scale) of each bolus, determined by VFSS 48 hours following the last investigational treatment, and converted to a trichotomized response as follows: Safe (PAS 1-3), Penetration (PAS 4-5), or Aspiration (PAS 6-8). Hypothesis testing will be a superiority test performed on the main effect of treatment, β_{trt} , i.e., the difference in cumulative log odds between treatment groups, with $\beta_{trt} > 0$ indicating the PES group has higher odds of a safer responses than the control group.

- Primary Efficacy Endpoint: The null hypothesis is that $\beta_{trt} \leq 0$ (PES does not result in safer swallows than the control treatment), and the alternative hypothesis is that $\beta_{trt} > 0$ (PES results in safer swallows than the control treatment).
- If the primary endpoint meets statistical significance then formal testing and analysis for the secondary endpoint will be carried out.

The analysis of the secondary endpoint of FIOS is based on a Cochran-Mantel-Haenszel (CMH), stratified by site and baseline PAS, using the modified ridit score and test of "row mean scores different" to take into account the ordered nature of the response.

The analysis of the secondary endpoint of DSRS is based on an ANCOVA model of mean DSRS 48 hours after the last study treatment, adjusting for baseline. Hypothesis testing will be a superiority test performed on the main effect of treatment, δ , with $\delta \ge 0$ indicating the PES group has lower mean DSRS than the control group.

• Secondary Efficacy Endpoint of DSRS: The null hypothesis for the $\delta \leq 0$ (PES does not result in lower DSRS), and the alternative hypothesis is that $\delta > 0$ (PES results in lower DSRS).

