4.2. Sample Size Justification

Sample size and power was determined through simulations. The study will follow an adaptive group sequential design with unblinded sample size re-assessment. In order to assure 180 evaluable patients with 7 day (+/- 1day) data and assuming a 20% dropout rate, approximately 225 patients will be enrolled initially. An interim analysis for futility (non-binding stop) will occur after the first 60 patients complete their 7 day visit, and another interim analysis will be performed for efficacy after 120 patients for futility stopping, early efficacy stopping on the primary endpoint and secondary endpoint, and sample size re-assessment (SSR). The total sample size may be increased up to approximately 338 patients after the second interim analysis to ensure up to 270 evaluable patients.

Based on prior feasibility studies (Bath et al., 2016) the primary endpoint is hypothesized to have an odds ratio of 2.23 favoring the PES group. For the secondary endpoint, the difference in mean DSRS between treatment groups is expected to be 1.75. A common standard deviation of 4 is assumed for DSRS in both treatment groups. With these effect sizes, the power is 95% for significance on the primary endpoint and 85% for significance on both endpoints. Additional simulation results under different assumptions are provided in the Simulation Report.

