4.5. Statistical Tests and Decisions at the Interim and Final Analyses

4.5.1. Test Statistics

For the primary endpoint, independent increments of the normally distributed Wald statistic $Z = \hat{\beta}_{trt}/\widehat{SE}(\hat{\beta}_{trt})$, calculated using the GEE method with a robust sandwich estimator, are used for hypothesis testing and conditional power (CP) calculations. For the secondary endpoint, independent increments of the normally distributed Wald statistic $Z = \hat{\delta}/\widehat{SE}(\hat{\delta})$ is calculated based on estimates of treatment effect and standard error from the ANCOVA model. Conditional power is defined as the probability of reaching statistical significance at the planned final analysis (N=180) conditional on the observed effect size, assuming the current observed effect size is the true effect size.

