4.5.3. Procedure at the second interim analysis

The second interim analysis is planned for when for when 120 patients complete their 7 day visit.

Efficacy stopping: An early efficacy stopping boundary of Z > 2.5093 (one-sided P < 0.0060) will be used for all efficacy endpoints. This boundary is the group sequential boundary derived from the Lan-DeMets O'Brien Fleming spending function at 2/3 information fraction. Early stopping for efficacy will be recommended only if both the primary endpoint and secondary endpoint cross the same boundary. If the study continues, both endpoints will be tested against the group sequential boundary 1.9929 at the final analysis in a sequential manner -- the secondary endpoint is tested if the primary endpoint reaches statistical significance -- to preserve the study-wise type 1 error rate at one-sided level 0.025.

If the study is not stopped for efficacy, the interim results will be classified into different zones depending on estimation of the conditional power on the primary endpoint and, separately, on the secondary endpoint. Based on the interim zone, one of the following actions will be recommended:

- Stop the study for futility (non-binding stop).
- Continue the study until reaching the planned 180 evaluable patients (approximately 225 enrolled).
- Continue the study and increase the sample size up to a maximum of 270 evaluable patients (approximately 338 enrolled).

Details on the boundaries of these interim zones and specific actions to be taken within these zones are deferred to a restricted Simulation Report whose circulation is limited to a core study team to include the ISC and DMC in order to minimize the possibility of operational bias.

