4.6.2 Secondary Efficacy Analysis

The secondary endpoints are FIOS and DSRS 7 days (+/- 1 day) after completion of investigational treatment.

The ordered categorical endpoint of FIOS will be analyzed by a Cochran-Mantel-Haenszel (CMH) test stratified by site and baseline PAS, using the modified ridit score and test of "row mean scores different" to take into account the ordered nature of the response.

The secondary endpoint of DSRS will be modeled by an ANCOVA model with treatment, center, baseline PAS and baseline DSRS as predictors, and will be tested for statistical significance provided the primary endpoint is found to be statistically significant. The ITT population will be used.

Missing data on the secondary endpoint will not be imputed for the purpose of significance testing.

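### Protocol 9.4.3 tests FOIS before DSRS; the SAP conditions DSRS on the primary endpoint only and never states the FOIS step

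*SAP*

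**What the plan says.** **Protocol 9.4.3** makes the secondary tests sequential once the primary is significant and names the order: "The first endpoint tested will be FOIS at 7 days following the last investigational treatment", then "The second endpoint tested will be DSRS at 7 days following the last investigational treatment". It leaves analysis details to the SAP.

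**SAP 4.6.2** lists both as secondary endpoints. FOIS (spelled FIOS) gets a stratified CMH test with no stated condition. DSRS gets an ANCOVA "and will be tested for statistical significance provided the primary endpoint is found to be statistically significant".

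**Other SAP sections:**
- 4.1 gates a single endpoint: "If the primary endpoint meets statistical significance then formal testing and analysis for the secondary endpoint will be carried out".
- 4.2 identifies it: "For the secondary endpoint, the difference in mean DSRS between treatment groups is expected to be 1.75". The 85% power for both endpoints is therefore for the primary plus DSRS.
- 4.5.1 defines Z-statistics for the primary and for one secondary endpoint. The latter "is calculated based on estimates of treatment effect and standard error from the ANCOVA model". Nothing is defined for the CMH test.
- 4.5.3 says the 2.5093 interim boundary "will be used for all efficacy endpoints", but adds: "Early stopping for efficacy will be recommended only if both the primary endpoint and secondary endpoint cross the same boundary". If the trial continues, one secondary endpoint follows the primary at 1.9929.
- 4.5.4 applies the combination statistic to the primary and secondary endpoints and prints 2.5093 as the final cut-off.
- 4.3.5 dismisses multiplicity, and section 5 declares no change from the protocol.

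Day-7 FOIS is also on the exploratory lists in Protocol section 3 and SAP 4.6.3, though not on the one in the protocol synopsis.

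**The concern.** A sequential procedure with a named first and second endpoint is ordinarily read as a fixed sequence: if FOIS is not significant, DSRS is not formally tested. The SAP sections that would be programmed describe two steps, primary then DSRS. Suppose the primary and DSRS succeed and FOIS does not. The SAP as written supports a DSRS claim, and the protocol order does not. This can arise at the second interim, where the joint crossing rule, read as DSRS, can end the trial before FOIS is significant.

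The SAP also leaves it open whether FOIS may be claimed alongside DSRS without an order. That would put two tests behind one gate. The study is meant to support a de novo submission, so what can be claimed on the secondaries should not be settled after the data are seen.

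**Working it through.** **1. The plan's boundaries.** Lan-DeMets O'Brien-Fleming spending at t = 2/3, one-sided 0.025:

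alpha spent = 2[1 − Φ(2.2414/√(2/3))] = 2[1 − Φ(2.745)] = 0.00605, so the interim cut-off is 2.5093.

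With correlation √(2/3) between looks, P(Z at interim > 2.5093 or Z at final > 1.9929) = 0.0250. Both figures in SAP 4.5.3 reproduce.

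**2. Error over the two secondaries.** Inputs: both secondaries null, primary effective (drift 3.64, which gives 95% power, or drift 8), primary-secondary correlation 0.3 or 0.5 (assumed), FOIS-DSRS correlation r (assumed). Protocol 8.1.8 describes both scales as scoring the result of the swallowing problem, so high r is plausible. Chance of at least one false secondary claim, in %:

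| FOIS and DSRS each opened by the primary, no order | r = 0 | 0.5 | 0.8 | 0.9 |
|---|---|---|---|---|
| Stop only if primary and DSRS cross; final 1.9929 | 4.71–4.76 | 4.33–4.38 | 3.74–3.78 | 3.38–3.43 |
| Each endpoint uses both looks in full; final 1.9929 | 4.94 | 4.54 | 3.91 | 3.53 |
| Each endpoint uses both looks in full; final 2.5093 | 1.96 | 1.85 | 1.61 | 1.45 |

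For comparison, at 1.9929: primary then DSRS, 2.5%; protocol order with an all-three stop, 2.3% to 2.4%.

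**3. What the 85% covers.** DSRS drift at 180 evaluable, SD 4, equal allocation assumed: 1.75/(4 × √(4/180)) = 1.75/0.596 = 2.93. DSRS alone at 90 per arm has 82.7% power at 1.9929. With primary power at 95%, joint power for primary and DSRS is 79% to 81% without sample size re-assessment. It is 85% to 87% with an assumed promising zone (conditional power 30% to 90% on either endpoint, N raised to 270). The stated 85% is thus plausible for primary plus DSRS with no FOIS step. It cannot be confirmed, because the zones are in the restricted Simulation Report.

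**4. How often the order matters (illustration only).** N = 180, no re-assessment, primary drift 3.64, DSRS drift 2.93, primary-secondary correlation 0.3, final cut-off 1.9929. The documents give no FOIS effect, so it is varied. Chance that primary and DSRS win and FOIS does not, r = 0.6 to 0.9:

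| Assumed FOIS strength | Stop needs primary and DSRS | Stop needs all three |
|---|---|---|
| Equal to DSRS (2.93) | 17% to 9% | 8% to 4% |
| 75% of DSRS (2.20) | 38% to 35% | 26% to 23% |
| Stronger (3.40) | 8% to 2% | 3% to 1% |

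In the first cell, 10 to 5 percentage points arise at the interim stop. With FOIS as strong as DSRS, the chance of a DSRS claim is about 80% under primary-then-DSRS and 71% to 76% under the protocol order.

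**The case against.** The best defence is that the documents can be read together. Protocol 9.4.3 never says outright that DSRS needs a significant FOIS. SAP 4.6.2 states a condition for DSRS without saying it is the only one. SAP 4.1 and 4.6.2 present FOIS before DSRS, and section 5 declares no change, so the SAP's silence might be taken as adopting the protocol order.

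Much of this stands. A reader might infer that one document flatly forbids a DSRS claim after a FOIS failure and the other flatly permits it. Neither text goes that far: the bar is the ordinary reading of a sequential order, and the permission comes from following the SAP as written. But the silence does not repair the plan. SAP 4.2, 4.5.1 and 4.5.3 set out a two-step scheme on DSRS, and FOIS has no Z-statistic with which to take part. Deferring details to the SAP does not cover an order the protocol sets itself.

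A reader might also infer that the study-wise error rate is broken. The documents do not support that. The excess needs both an unordered reading and the 1.9929 cut-off, and it vanishes at 2.5093.

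Finally, the 17% to 9% figure presupposes an early stop on primary and DSRS alone. It roughly halves if all three must cross, and it depends on an assumed FOIS effect.

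**Conclusion.** The inconsistency is real and should be fixed. The protocol gives a three-step order, the SAP describes a two-step one ending in DSRS, and section 5 says nothing changed. The consequence is limited to the secondary claims.

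- Each scheme alone, primary-then-DSRS or the protocol order, holds one-sided 0.025.
- The chance of a false secondary claim rises to about 3.4% to 4.8% (correlation 0.9 to 0) only if both secondaries are null, both are opened by the primary without an order, and the final cut-off is 1.9929.
- The frequency with which the order decides a DSRS claim cannot be fixed from the documents. With FOIS as strong as DSRS it is 17% to 9% or 8% to 4%, depending on the stop rule. A weaker FOIS effect raises these figures and a stronger one lowers them.

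The textual finding does not rest on the assumed FOIS effect or correlations.

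**What to change.** Before the first unblinded interim, write one fixed sequence into SAP 4.1, 4.3.5, 4.5.3, 4.5.4 and 4.6.2. Either:

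- (a) keep the protocol's primary, FOIS, DSRS; or
- (b) use primary, DSRS, then FOIS, amend Protocol 9.4.3, and record the change in SAP section 5.

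In either case:
- State which secondary endpoint or endpoints must cross for the early efficacy stop. The endpoint for sample size re-assessment needs no decision, since Protocol 9.2 already names day-7 DSRS.
- Define in SAP 4.5.1 the FOIS Z-statistic for each look, in a form that fits the combination statistic.
- Remove day-7 FOIS from the exploratory lists in Protocol section 3 and SAP 4.6.3.
- State that the 85% power is for primary plus DSRS without a FOIS step.

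The conflict between final cut-offs 1.9929 and 2.5093 is a separate correction, but it determines the error figures above.

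The cost is SAP wording, plus a short protocol amendment under (b). Option (a) lowers the chance of a DSRS claim, from about 80% to 71% to 76% in the illustration with FOIS as strong as DSRS.

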4.6.3 Exploratory Efficacy Analysis

Exploratory endpoints are as follows:

- The severity of unsafe swallows will be further evaluated via:
 - o PAS outcome by each consistency (thin and nectar)
 - o Physiologic measurement obtained using the Modified Barium Swallow Impairment Profile (MBSImP) metrics will be extracted from the thin and nectar swallows by the core lab by using the baseline and follow up VFSS data. These validated and reliable metrics of critical swallowing movements will be explored for their relationship to the primary study endpoint (PAS).
 - o PAS dichotomized as safe (PAS 1-3) or unsafe (PAS 4-8)
- Nutritional management changes will be evaluated via:

- Dysphagia Severity Rating Scale (DSRS) at 14 days or discharge, whichever is first, and at 11 weeks following the last investigational treatment.
- Time from baseline to removal of enteral feeding (i.e., removal of NG tube or PEG or transition to oral feeding, or first diet upgrade)
- Functional Oral Intake Scale (FOIS) at 7 days, 14 days or discharge, whichever is first, and 11 weeks following the last investigational treatment
- Quality of life (QOL) will be assessed baseline and 11 weeks following the last investigational treatment via the following instruments
 - EuroQoL-5 Dimension Questionnaire (EQ-5D) and EuroQoL-Visual Analogue Scale (EQ-VAS).
- General stroke health outcomes assessed by:
 - o Time to discharge from site in which treatment is received
 - o Discharge destination from the site in which treatment is received
 - o Patient location (home, institution) at 11 weeks
 - Days on antibiotics during hospital stay
 - NIH Stroke Scale (NIHSS) at baseline and 14 days or discharge, and 11-week follow up
 - o Modified Rankin Scale (mRS) at baseline, 14 days, and 11 week follow up
 - o Barthel Index (BI) at baseline, 14 days or discharge, and 11-week follow up
 - New onset pneumonia, using a standardized definition adapted from the STROKE-INF study²⁶ at baseline, 48 hrs, 7 days, and 14 days or discharge
 - Hospital readmission rate
 - o Number of CXR (related to suspect pneumonia)

Exploratory endpoints will be summarized by treatment group, and may be analyzed using appropriate statistical models with adjustments for key prognostic covariates. No multiplicity adjustments will be made for exploratory analyses.

For time-to-event endpoints, Cox proportional hazards models which includes effects for treatment, center and baseline PAS will be used. In addition, the Kaplan-Meier estimates of time to first event will be presented for each treatment group. Kaplan-Meier plot of time to first event (survival function) will also be presented by treatment groups.

For continuous endpoints, ANCOVA models with the effects of treatment group, center, baseline PAS and the baseline value of that variable will be used.

For nominal categorical endpoints, a Cochran-Mantel-Haenszel (CMH) test stratified by site and baseline PAS will be used. The ordered categorical endpoint of mRS will be analyzed by a CMH test stratified by site and baseline PAS, using the modified ridit score and test of "row mean scores different" to take into account the ordered nature of the response.

For hospital readmission rate, a Poisson model with the effects of treatment group, center, baseline PAS and using patient-year as the offset will be used.

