CONFIDENTIAL Page 16 of 71

Pooling the few studies with sufficient data to allow this, the presence of dysphagia conferred a relative risk (RR) of 3.17 (95% CI, 2.07-4.87) for developing pneumonia, and the RR increased more than three-fold among patients with confirmed aspiration (RR, 11.56; 95% CI; 3.36-39.77).

Katzan et al.'s, retrospective analysis indicated that pneumonia conferred a relative risk for 30-day mortality that was six time greater for patients with pneumonia than without (26.9% vs. 4.4%, p<0.001)³. After adjusting for independent factors, the RR for 30-day mortality was still almost 3 times greater for patients with pneumonia (2.99; 95% CI, 2.44 to 3.66). The authors estimate that 10% of all deaths following stroke are attributable to pneumonia.

The studies that specifically assessed post-stroke dysphagia demonstrate that the presence of dysphagia also confers a greater relative risk of poor outcome. Specifically, Dziewas et al., found that dysphagic patients who developed pneumonia needed the NGT to remain in place for a longer period of time, with a median of 15 vs. 2 days or an average of 16.3 ± 7.2 vs. 4.9 ± 4.8 days (p<0.001) for patients with pneumonia vs. those without. Dziewas et al., found among those having a poor 3-month outcome (modified Rankin Score (mRS) \geq 4), had a higher incidence of pneumonia during their hospital stay than did those that had a good (mRS \leq 1) or moderate (mRS = 2 or 3) outcome, at 70% vs. 23% and 24%, respectively. Duration of enteral feeding was also longer in patients with a poor outcome at 3 months⁵.

Smithard et al., and Arnold et al., also report that the presence of dysphagia is associated with longer hospital stays and higher mortality. Mortality was 37% for patients with dysphagia vs. 6% for those without dysphagia among patients reported on by Smithard et al., and the presence of dysphagia was a significant predictor for mortality after adjusting for confounding variables⁴. In the 2016 report by Arnold et al., mortality was 27% among patients with dysphagia vs. 7.4% for those without. The risk of death was higher for the subgroup of dysphagic patients requiring tube feeding. The occurrence of pneumonia was only weakly associated with mortality risk⁷.

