4.3. General Statistical Methods and Data Handling

4.3.1. General Methods

All output will be incorporated into Microsoft Excel or Word files, sorted and labeled according to the International Conference on Harmonisation (ICH) recommendations, and formatted to the appropriate page size(s).

Tabulations will be produced for appropriate demographic, baseline, efficacy and safety parameters. For categorical variables, summary tabulations of the number and percentage within each category (with a category for missing data) of the parameter will be presented. For continuous variables, the mean, median, standard deviation, minimum and maximum values will be presented. Time to event data will be summarized using Kaplan-Meier Methodology using 25th, 50th (median), and 75th percentiles with associated 2-sided 95% confidence intervals, as well as percent of censored observations.

Formal statistical hypothesis testing will be performed on the primary and secondary efficacy endpoints with all tests conducted at the 1-sided, 0.025 level of significance. Summary statistics will be presented, as well as confidence intervals on selected parameters, as described in the sections below.

For all analyses, baseline will be defined as the most recent measurement prior to the date and time of the administration of active treatment with Pharyngeal Electrical Stimulation or a sham treatment. Therefore, baseline may be on the same day as the start of study treatment, but prior to the administration of the study treatment.

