4.3.8. Missing, Unused, and Spurious Data

In general, there will be no substitutions made to accommodate missing data points. All data recorded on the CRF will be included in data listings that will accompany the clinical study report.

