4.8. Efficacy Evaluation

4.6.1 Primary Efficacy Analysis

The primary endpoint is trichotomized PAS on each bolus, determined by VFSS 48 hours (+/- 24 hours) after completion of PES treatment. The three ordinal PAS categories are defined as Safe (PAS 1-3), Penetration (PAS 4-5), and Aspiration (PAS 6-8). Each patient contributes 12 measurements to the primary endpoint, of which six are from boli of a thin consistency and 6 are from boli of a nectar consistency.

The ITT population will be used for the primary analysis.

A cumulative logistic model will be used to analyze the primary endpoint, and a sandwich variance estimator via a generalized estimating equations approach will be used to account for correlated PAS outcomes within each patient.

The statistical model for the primary analysis will include treatment, bolus consistency, baseline maximum PAS, and treatment by consistency interaction as predictors. The response of individual i on bolus t is coded as $y_{it} = 1$ for a safe swallow, $y_{it} = 2$ for a swallow resulting in penetration, and $y_{it} = 3$ for a swallow resulting in aspiration. The log odds of a swallow with response $\leq j$ conditional on predictors x_{it} is modeled as

$$logit(P(y_{it} \le j | x_{it}))$$

$$= \beta_j + \beta_{base} * base_{it} + \beta_{trt} * trt_i + \beta_{nectar} * nectar_t + \beta_{trt*nectar} trt_i * nectar_t$$

with ordered intercept terms $\beta_1 < \beta_2$, a treatment indicator trt_i (1=PES, 0=control), and a consistency indicator $nectar_i$ (1=nectar, 0=thin). The maximum PAS (1-8) of individual i across all pre-treatment swallows of a given consistency at baseline is denoted $base_{it}$. The GEE approach with robust sandwich estimator is used to account for within subject correlation.

Missing PAS data will be imputed in the primary analysis. PAS values that are missing due to application of VFSS stopping criteria will be assigned the worst (highest) post-treatment PAS value. For patients who have no post-treatment PAS data due to lost-to-follow-up or death, the post-treatment PAS values will be imputed from baseline PAS values and other patient baseline characteristics using multiple imputation. In addition, tipping point analysis will be performed as a sensitivity analysis.

The estimated treatment effect in the logistic model will be presented along with standard error. The treatment effect will also be presented as an odds ratio with 95% confidence interval.

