4.9.1. Adverse Events

Adverse events will be coded using the Medical Dictionary for Regulatory Activities (MedDRA) and displayed in tables and listings using System/Organ/Class (SOC) and Preferred Term.

Analyses of adverse events will be performed for those events that are considered treatment emergent, where treatment emergent is defined as any adverse event with onset after the administration of study medication through the end of the study, i.e. 30 days after the surgery or any event that was present at baseline but worsened in intensity or was subsequently considered drug-related by the investigator through the end of the study.

Adverse events are summarized by subject incidence rates, therefore, in any tabulation, a subject contributes only once to the count for a given adverse event (SOC or preferred term).

The number and percentage of subjects with any treatment-emergent adverse event, with any treatment-emergent adverse events assessed by the Investigator as related to treatment (definite, probable, or possible relationship), and with any serious adverse event will be summarized by treatment group and overall. In these tabulations, each subject will contribute only once (i.e., the most related occurrence or the most intense occurrence) to each of the incidence rates in the descriptive analysis, regardless of the number of episodes.

No formal hypothesis-testing analysis of adverse events incidence rates will be performed.

All adverse events occurring on study will be listed in subject data listings.

By-subject listings also will be provided for the following: subject deaths; serious adverse events; and adverse events leading to withdrawal.

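### Patient location at 11 weeks has no rule for patients who die, so the planned comparison would be among survivors only and could flatter an arm with more deaths

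*SAP*

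**What the plan says.** SAP 4.6.3 lists the endpoint as "Patient location (home, institution) at 11 weeks". Protocol section 3 gives the same two values, and neither document mentions death in connection with location.

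Three general rules bear on it:

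- SAP 4.6.3, on testing: "For nominal categorical endpoints, a Cochran-Mantel-Haenszel (CMH) test stratified by site and baseline PAS will be used". The same section makes modeling of exploratory endpoints optional and adjusts none of them for multiplicity.
- SAP 4.3.8, on missing data: "In general, there will be no substitutions made to accommodate missing data points".
- SAP 4.3.1, on categorical tables: "summary tabulations of the number and percentage within each category (with a category for missing data) of the parameter will be presented".

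Death is dealt with elsewhere in the plan. For the primary endpoint, SAP 4.6.1 provides multiple imputation, in a sentence that opens "For patients who have no post-treatment PAS data due to lost-to-follow-up or death". The mRS has death as level 6 (Protocol 8.1.5), and SAP 4.6.3 tests it with a CMH test on row mean scores. On the safety side, SAP 4.9.1 states: "By-subject listings also will be provided for the following: subject deaths; serious adverse events; and adverse events leading to withdrawal".

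**The concern.** A patient who has died is neither at home nor in an institution. With only those two values, no substitution and a CMH test on the observed categories, that patient contributes nothing to the test. Death before week 11 is an outcome that follows randomization. Removing it leaves a comparison of survivors, which randomization no longer protects.

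The likely direction is awkward. If the patients who die are mostly those who would otherwise have been in an institution, each extra death removes an unfavorable location from the denominator and raises the percentage at home. An arm could then look better on discharge home because more of its patients died. What is at stake is a misleading supportive result, not the trial's main claim.

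**Working it through.** **1. The plan's own figures.** The documents state no number for this endpoint, so the only figures to reproduce are the sample sizes. 180/(1 − 0.20) = 225, and 270/(1 − 0.20) = 337.5, rounded up to 338. Both match SAP 4.2. For illustration I use 225/2 = 112.5, taken as 112 per arm. The 1:1 ratio is my assumption.

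**2. Formulas.** Let N be the number randomized per arm, D the deaths by week 11 and h the number at home.

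- Percentage at home among survivors = h/(N − D).
- Percentage alive and at home among all randomized = h/N.
- In an institution = N − D − h. With h equal in both arms, the survivor odds ratio is the institution count in the arm with fewer deaths divided by that in the arm with more.

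Assumptions not in the documents: h is the same in both arms, and the extra deaths come only from patients who would otherwise be in an institution. The p-values are from an unstratified Pearson chi-square without continuity correction.

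**3. Results with h = 56 of 112 (50%) in each arm.**

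| Deaths, higher vs lower arm | Counts | At home among survivors | Gap | Odds ratio | p |
|---|---|---|---|---|---|
| 10% vs 5% | 11 vs 6 | 56/101 = 55.4% vs 56/106 = 52.8% | 2.6 points | 50/45 = 1.11 | 0.71 |
| 20% vs 10% | 22 vs 11 | 56/90 = 62.2% vs 56/101 = 55.4% | 6.8 points | 45/34 = 1.32 | 0.34 |
| 27% vs 15% | 30 vs 17 | 56/82 = 68.3% vs 56/95 = 58.9% | 9.3 points | 39/26 = 1.50 | 0.20 |

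In every row the all-randomized percentage is 56/112 = 50.0% in both arms, a difference of zero.

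If the share at home is varied from 40% to 60%, the gap runs from 2.1 to 3.1 points for deaths of 10% vs 5%, and from 5.4 to 8.1 points for 20% vs 10%.

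**4. Which death rates are plausible.** The documents give none for this trial. Protocol 2.1 cites two reports in stroke: "mortality was 27% among patients with dysphagia vs. 7.4% for those without" and "Mortality was 37% for patients with dysphagia vs. 6% for those without dysphagia". It also cites a single-center study with five deaths in six months among 117 patients with data, or 5/117 = 4.3%. All five were dysphagic. On that study's baseline counts of 65 (clinical) or 82 (videofluoroscopy) dysphagic patients, this is roughly 5/65 = 7.7% or 5/82 = 6.1%. These are approximate, because the counts come from the full cohort of 128. This trial enrolls 7 to 28 days after stroke and excludes tracheostomy, current pneumonia treatment and the highest NIHSS scores, so the lower rows of cited mortality may be the closer guide.

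**The case against.** The exclusion of deaths is inferred. A reader might take the SAP to say that deaths are removed from this endpoint, but it does not say so. By SAP 4.3.1 they could appear in the summary table, in the missing-data category. That stands as a limit on the wording. It does not close the gap: deaths would be mixed with losses to follow-up in that category, and the CMH test, if run, has no value to give them.

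Deaths also stay visible elsewhere. They are level 6 of the mRS at the same visit, they count as serious adverse events summarized by arm, and they are listed. This makes it less likely that an excess of deaths would pass unnoticed, but it does not correct the location comparison.

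The size rests on assumptions. Nothing in the documents suggests that PES raises mortality. A reader might place the cited 27% and 7.4% in the two arms as a realistic contrast, but those are rates for patients with and without dysphagia. That deaths come mainly from would-be institution patients is plausible: Protocol 2.1 reports a higher risk of death in tube-fed dysphagic patients and links dysphagia to institutionalization at 3 months. It is not shown. If deaths instead fell evenly on both groups, the survivor percentages would not be distorted upward.

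A reader might also extend the point to discharge destination, or conclude that every other 11-week scale needs deaths scored as the worst rank. The documents do not list the categories of discharge destination, so no omission can be shown there. Worst-rank scoring would change what those scales estimate; it is a trade-off, not the repair of an error.

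**Conclusion.** The point holds as a low-severity gap. No rule classifies patients who die before the 11-week location assessment, and the rules that do exist lead to a survivors-only test.

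If deaths differ by arm and come mainly from patients who would otherwise be in an institution, the arm with more deaths gains about 2.6 points on percentage at home for deaths of 10% vs 5%, and about 7 points for 20% vs 10%, when half of each randomized arm is at home. The difference among all randomized is zero. These are illustrations, since neither the death rate nor the home rate is given for this trial.

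A reader might infer that the trial's efficacy claim is at risk. It is not: the endpoint is exploratory, its testing is optional, and it touches no alpha, sample size, interim decision, or primary or secondary conclusion.

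**What to change.** In SAP 4.6.3:

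- Define location at 11 weeks as home, institution or dead, in that order, on all randomized patients.
- Test it with the stratified row-mean-scores CMH already specified for mRS. An acceptable alternative is a two-level endpoint, alive and at home versus not, on all randomized patients.
- Tabulate the three categories by arm, with locations missing for other reasons on a separate line, and state how those are handled in the test.

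The cost is a few lines of SAP text, best settled before unblinding. Deaths are already collected as serious adverse events and are needed for mRS level 6.

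There are two small downsides. The endpoint then combines residence and survival, which is why the three-way table should go with it. Vital status may also be unknown for some patients: Protocol 7.2 allows for loss to follow-up, and Protocol 10.3 asks only for an attempt to obtain permission to collect vital status when authorization is revoked.
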